2. SAMPLE SIZE

Treatment effect and subject variability with respect to SOWS-Gossop scores were estimated from the prior Phase 3 study (USWM-LX1-3002), using the random coefficients model planned for the present study and estimating the treatment effect of 3.2 mg lofexidine versus placebo with respect to area under the curve (AUC) based on the SOWS-Gossop scores from Days 1 through 7 (AUC(1-7)). It was assumed that the treatment effect of the 2.4 mg lofexidine dose will be three-fourths the treatment effect of the 3.2 mg dose. The table below shows the power to find a significant treatment effect for the comparisons of the two lofexidine treatments versus placebo, assuming a sample size allocation ratio of 3:3:2 (3.2 mg lofexidine : 2.4 mg lofexidine : placebo) and accounting for the sequential testing approach described in Section 6.1. The power to find a statistically significant effect of the 3.2 mg lofexidine dose with respect to AUC (1-7) is in excess of 90% with the planned total sample size of 600.

	Power (%) with Respect to AUC (1-7)		
Total Sample Size	3.2 mg Lofexidine versus Placebo	2.4 mg Lofexidine versus Placebo	
600	94.6	72.6	
550	92.6	67.6	
500	90.1	62.2	
450	86.8	55.7	

Effective: 14-Feb-13

Page 4 of 26

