6.12 Multiplicity

For the primary and secondary endpoints, the treatment comparisons subject to control of the false positive rate will be 3.2 mg lofexidine vs. placebo and 2.4 mg lofexidine vs. placebo. Comparisons of 3.2 mg vs. 2.4 mg will be descriptive. The familywise error rate (FWE) for the collection of primary and secondary endpoint comparisons will be controlled at the 0.05 level, two-sided, by a sequential testing strategy in which hypotheses are tested in the following order, each at the 0.05 level, using a two-sided test.

- 1. Primary: AUC(1-7), 3.2 mg lofexidine versus placebo;
- 2. Primary: AUC(1-7), 2.4 mg lofexidine versus placebo;
- 3. Secondary: Completion rate, 3.2 mg lofexidine versus placebo; and
- 4. Secondary: Completion rate, 2.4 mg lofexidine versus placebo.

The tertiary/exploratory endpoints will be tested without multiplicity adjustment.

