It will be assumed that subjects randomized to lofexidine who withdraw from the study will have a time trajectory comparable to placebo post withdrawal. The pattern-mixture model will be implemented using multiple imputations (Ratitch⁶, 2011). The imputation of missing values and the analysis will be performed multiple times (20 imputed datasets) with the initial seed value set at '123', and the inference of this sensitivity analysis will be based on the combined estimates using the standard multiple imputation technique. This method is detailed in the section entitled "Pattern-Mixture Model with Control-Based Pattern Imputation" (Ratitch⁷, 2013). Briefly, the initial step is to impute the relatively rare, non-monotone missing data via the MCMC Option of SAS® PROC MI. This step uses iterative methods, with which non-convergence is a possibility; should an MCMC imputations that converge will be used in the analysis. This imputation model will be implemented for each combination of gender and treatment. (It should be noted that by performing the imputation for each such combination, the imputation modelling will be richer than the model used to inferentially analyse the data. It is acceptable, even preferable, for the imputation model to be richer than for the analysis model (see Little and Rubin, 2002).

The next step applies to the monotone missing data. The values for each pattern will be imputed using the chained equation method by SAS® PROC MI option MONOTONE REG. This MNAR imputation employs only the appropriate data for each pattern. That is, the missing data for lofexidine treatment arm at time t will be imputed using only the data on placebo subjects up to time t and the data for lofexidine subjects who have data up to time t-1 but are missing data at time t. The model for imputing missing data at time t will include fixed effect terms for study day from the baseline visit through to the t-1 visit and sex. Note that a term for treatment group is not included in this imputed data sets will be analyzed using the MMRM model described below and then summarized using PROC MIANALYZE. The model will include fixed effects for treatment group, baseline log_e (SOWS-Gossop score +1), sex, study day (days 1-7), and

Effective: 24-Dec-2014

Page 7 of 29

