treatment group-by-day interaction. In this model the treatment group term in the model represents the effect of treatment over days 1 to 7. An unstructured covariance model will be used. However, in the event that this model does not converge then the following covariance models will be used in order until the model converges: Toeplitz, first-order autoregressive and compound symmetry. Analysis will be performed using PROC MIXED in SAS and the resultant F-tests will be based on Kenward-Roger's adjusted degrees of freedom.

Justification

Fitting an MMRM analysis without the imputation described above would have entailed an assumption that the missing data are missing at random (MAR). The combined process of imputation followed by MMRM does not assume MAR and provides an unbiased estimate of the treatment effect that follows under the assumption that the mechanism by which data are missing not at random (MNAR) is that upon withdrawal from the study, the SOWS-Gossop trajectory of subjects randomized to lofexidine evolves as the trajectory of placebo subjects.

Change 8

Section 6.9.1 Sensitivity Analysis

The text in bold has been edited:

The following sensitivity analyses will be conducted:

- \neq The above analysis will be performed using the per-protocol population.
- ≠ The log_e (SOWS-Gossop score plus 1) from day 1 to day 7 will be analyzed using a MMRM model on the mITT population.

The model will include fixed effects for treatment group, baseline log_e (SOWS-Gossop score plus 1), sex, study day (days 1-7) and treatment group-by-day interaction. In this model the treatment group term in the model represents the effect of treatment over days 1 to 7. An unstructured covariance model will be used. However, in the event that this model does not converge then the following covariance models will be used in order until the model converges: Toeplitz, first-order autoregressive and compound symmetry. Analysis will be performed using PROC MIXED in SAS and the resultant F-tests will be based on Kenward-Roger's adjusted degrees of freedom. This MMRM analysis assumes that the missing data are missing at random (MAR). This analysis provides an unbiased estimate of the treatment effect that would have been observed had all subjects continued

Effective: 24-Dec-2014

Page 8 of 29

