on treatment until day 7. It therefore assumes that the response for withdrawn subjects would have followed the trajectory of the respective treatment after discontinuation, had they not withdrawn.

- In a further sensitivity analysis on the mITT population a "tipping point analysis" (Ratitch⁷, 2013) will be conducted in order to understand the "tipping point" δ at which the conclusions change from being statistically significant at the α =5% level using a 2sided test in favor of lofexidine to not statistically significant. This sensitivity analysis as per the sensitivity analysis described above begins with an imputation of the relatively rare non-monotone missing data using the MCMC option of PROC MI, based on standard MAR assumptions. The random seed for this set of analyses will be '456'. Then several analyses will be performed, indexed by the value δ , in each of which all monotone missing values are imputed using standard MAR assumptions, except in the imputation model in this instance will also include a covariate for **treatment.** In the first such analysis $\delta = 0$, which effectively is last observation carried forward. In general, δ is the adjustment that is added to the log_e (SOWS-Gossop score +1) at each visit after dropout during imputation. This increment is only added to the missing visits for the lofexidine groups. Delta is increased in increments of 1 (on the original SOWS-Gossop scale, before log transformation) until the point at which the comparison for the lofexidine group to placebo loses statistical significance. (An increment of 1 is selected, because the SOWS-Gossop scale ranges from its lowest to highest score by consecutive integers.) Effectively this analysis provides the amount by which the lofexidine subjects who discontinued early would need to be worse at each visit for the null hypothesis of no treatment difference to no longer be rejected. The imputed datasets are analyzed with the same MMRM model used in the primary analysis. The results are analyzed using PROC MIANALYZE.

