It will be assumed that subjects randomized to lofexidine who withdraw from the study will have a time trajectory comparable to placebo post withdrawal. The pattern-mixture model will be implemented using multiple imputations (Ratitch⁶, 2011). The imputation of missing values and the analysis will be performed multiple times (20 imputed datasets) with the initial seed value set at '123', and the inference of this sensitivity analysis will be based on the combined estimates using the standard multiple imputation technique. This method is detailed in the section entitled "Pattern-Mixture Model with Control-Based Pattern Imputation" (Ratitch⁷, 2013). Briefly, the initial step is to impute the relatively rare, non-monotone missing data via the MCMC Option of SAS® PROC MI. The imputation model will include as predictors an indicator variable for gender (1 d.f.), two indicator variables for treatment (2 d.f), the Baseline value, and variables for Day 1 through Day 7 data. This step uses iterative methods, with which nonconvergence is a possibility; should an MCMC imputation step not converge, alternative models will be developed by dropping time point variables from the model, one at a time starting at Day 7, until convergence is achieved. For example, if non-convergence occurs for the model that includes all the time point variables from baseline through Day 7, the next model to be considered will have all time point variables from baseline through Day 6, as well as the indicators for treatment and gender. The next model, if needed, would have all time point variables from baseline through Day 5, and so forth. Should this approach not succeed, ad hoc methods to impute non-monotone missing data will be developed and documented.

These contingency models for non-convergence, as well as the modeling of data with a monotone missing pattern, will require additional random number seeds. As stated in the SAP, the seed for the first step of the monotone missing imputation is '234'. The following additional seeds are to be used in the order shown for any additional modeling of non-monotone missing data as well as for the subsequent imputation of monotone missing data.

Effective: 22-Jan-2015

Page 6 of 11

Protocol Number USWM-LX1-3003-1 Statistical Analysis Plan Addendum 2 Version: Final Issue Date: 22-Jan-2015

- 1. 345
- 2. 456
- 3. 567
- 4. 678
- 5. 789
- 6. 890
- 7. 901
- 8. 012
- 9. 124
- 10.245
- 11.356
- 12.467
- 13. 578
- 14.689
- 15.790
- 16.145
- 17.256

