- 18.367
- 19.478
- 20.589

Effective: 22-Jan-2015

Page 7 of 11

Justification

To acknowledge the possibility of non-convergence and to clarify a process to implement systematic adjustments to the model to achieve convergence. To simplify the imputation model by modeling the entire data set once rather than for each separate combination of treatment and gender. To pre-specify a list of random number seeds for use in the imputation process.

Effective: 22-Jan-2015

Page 8 of 11

Effective: 22-Jan-2015

Page 9 of 11

Effective: 22-Jan-2015

Page 10 of 11

Approval for implementation of

Fitle:	A Phase 3, Randomized, Multicenter, Double-Blind, Placebo-Controlled, Efficacy, Safety and Dose-Response Study of Lofexidine in the Treatment of Opioid Withdrawal (Days 1-7) Followed by Open-Label, Variable Dose Lofexidine Treatment (Days 8-14)
Reference:	USWM-LX1-3003-1/SAP Addendum/1
Addendum No:	2
Date effective:	22-Jan-2015
Author:	Principal Statistician
reviewer:	Principal Statistician
Author's signature:	Date:
Reviewer's signature:	Date:
The above Statistical Ar Sponsor:	nalysis Plan Addendum has been reviewed and approved by the
Name of Approver: Position:	Medical Director, US WorldMeds, LLC
Signature:	Date:
Name of Approver:	
Position:	Sr. Manager, Biometrics, US WorldMeds, LLC
Signature:	Date:

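### The principal analysis pools only 20 imputed datasets with no check on Monte Carlo error, so avoidable noise enters a gated 0.05 test

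*SAP*

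**What the plan says.** Addendum 1, Change 7 replaced the earlier AUC model with control-based multiple imputation followed by a repeated-measures model. Addendum 2, Change 6 revised the imputation step and kept the number of datasets: the work "will be performed multiple times (20 imputed datasets) with the initial seed value set at" 123, and inference "will be based on the combined estimates using the standard multiple imputation technique". Addendum 2 also added fallbacks for non-convergence and a seed list, giving as one reason "To pre-specify a list of random number seeds for use in the imputation process".

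The tested quantity is an average over the week: "the treatment group term in the model represents the effect of treatment over days 1 to 7" (Addendum 1, Change 7). Under SAP 6.12, "hypotheses are tested in the following order, each at the 0.05 level, using a two-sided test". Addendum 1, Change 6 restates the gate for the new endpoint: 3.2 mg must succeed before 2.4 mg can be claimed. The completion-rate tests follow.

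For the tipping-point analysis (Addendum 1, Change 8), "The random seed for this set of analyses will be" 456, but the number of imputed datasets is not stated. The text there refers back to the sensitivity analysis described before it.

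**The concern.** Twenty imputations are a random sample from the imputation distribution. A different, equally valid list of seeds would give a different pooled estimate, standard error and p-value from the same trial data. If the long-run p lies near 0.05, that noise alone can decide on which side the reported p falls, and so whether the next hypothesis may be tested. Pre-specified seeds stop anyone choosing a favourable run, but the one run allowed is just as noisy.

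The tipping-point delta is read off where p crosses 0.05, so that analysis works in the sensitive region by construction.

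Unlike sampling error, this noise can be removed without recruiting anyone.

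**Working it through.** **1. Inputs from the plan.** M = 20; two-sided alpha 0.05; 225:225:150 subjects; power at N = 600 of 94.6% (3.2 mg) and 72.6% (2.4 mg); and the assumption that "the treatment effect of the 2.4 mg lofexidine dose will be three-fourths the treatment effect of the 3.2 mg dose" (SAP 2). The power table was built for the earlier AUC model. No figure in the plan is tied to M = 20.

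**2. Reproducing the power table.** Effect size and SD are not given, so the noncentrality is back-solved from the first row:

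- 3.2 mg: 1.96 + z(0.946) = 1.96 + 1.61 = 3.57. Scaling by sqrt(N/600) gives 92.7, 90.3 and 87.1% at N = 550, 500 and 450, against the stated 92.6, 90.1 and 86.8.
- 2.4 mg: 0.75 x 3.57 = 2.68, a marginal power of 76.3%. Multiplying by the 3.2 mg power, 0.946 x 0.763 = 72.2%, against the stated 72.6%.

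These noncentralities are close enough to use in step 6.

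**3. Formula.** With W and B the within- and between-imputation variances, Rubin's total variance is T = W + (1 + 1/M)B. The Monte Carlo standard error of the pooled estimate is sqrt(B/M). Writing r = B/T, for a z near 1.96:

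Var(z) = r/M + (1.96²/4) x 2r²/(M-1)

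The first term is noise in the estimate, the second noise in its standard error.

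**4. Size of r.** The documents give no dropout rate, so this is assumed: dropout by Day 7 of 20-70% on placebo and 15-55% on lofexidine; early, even or late; two correlation structures. Control-based sequential regression imputation was simulated with 150/225/225 subjects. The 7-day mean was analysed with treatment, baseline and sex, as an approximation to the repeated-measures model. There were 24 scenarios, 8 datasets each and 10,000 imputations per dataset, split into disjoint groups of M. The result was r = 0.03 to 0.26. Timing matters because the contrast averages seven days: at 70%/55% dropout, r was 0.11 if late and 0.26 if early.

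**5. Noise in z and p.** By formula at M = 20:

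- r = 0.03: sqrt(0.0015 + 0.00009) = 0.040
- r = 0.26: sqrt(0.0130 + 0.0068) = 0.141

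| M | SD of z (simulated) | Central 95% of p, light late dropout | Central 95% of p, heavy early dropout |
|---|---|---|---|
| 20 | 0.04-0.15 | 0.042-0.060 | 0.025-0.099 |
| 100 | 0.02-0.07 | not tabulated | not tabulated |
| 500 | 0.01-0.03 | 0.048-0.052 | 0.043-0.057 |

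The p ranges are simulated, with the long-run p set to 0.05. The formula gives 0.042-0.060 and 0.025-0.092 at M = 20, so the two agree closely.

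**6. Unconditional effect on the decision.** This is the chance that a run of M and the long-run answer fall on opposite sides of 0.05, averaged over trials at the noncentralities in step 2:

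| | M = 20 | M = 500 |
|---|---|---|
| 3.2 mg (3.57) | 0.4-1.4% | 0.1-0.3% |
| 2.4 mg (2.68) | 1.0-3.9% | 0.2-0.8% |

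A normal approximation using the formula gives 0.35-1.2% and 0.98-3.5% at M = 20.

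**7. Tipping point, if M = 20 is used there.** Imputation under MAR with treatment, delta in 1-point steps, one correlation structure, even dropout timing, 3 dropout rates, 14 datasets each, 1,000 imputations. The share of runs reporting a delta different from the long-run one was 20%, 16% and 8% from light to heavy dropout, almost always by one step.

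**8. Check without simulating the imputation.** Taking the fraction of missing information (FMI) as 0.1-0.5, Monte Carlo SE/SE = sqrt(FMI/M): 7.1-15.8% at M = 20 and 1.0-2.2% at M = 1000. Type I error was 0.050 at both. Moving to M = 1000 raised power by 0.1-1.1 points (3.2 mg) and 0.2-2.2 points (2.4 mg). This FMI range extends above the simulated r, so it supports the direction and is not used for the size.

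**The case against.** The plan contains no error. M, seeds, pooling rule and test order are all fixed in advance. Rubin's rules allow for finite M, so the test at M = 20 is a valid 5% test. A run of 20 that disagrees with the long-run answer is a disagreement between two valid tests, and it can go either way. **This stands**, and it is why no bias or type I error inflation is claimed.

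The widest p range needs a long-run p of exactly 0.05 together with heavy, early dropout. At the planned effect only about 6% of trials would give a 3.2 mg p between 0.025 and 0.099, and about 18% a 2.4 mg p in that range. **This also stands**; the unconditional figures in step 6 are the ones that bear on the decision.

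The size rests on assumed dropout and on an effect taken from the superseded AUC model. The simulation did not explicitly model two rules that reduce missingness: assigning discontinuation-visit scores to their actual day, and prorating missing items (Addendum 2, Changes 5 and 1). They could lower r somewhat, so the heavy-dropout end may be overstated. The noise would still be there.

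For the tipping point, 80-92% of runs gave the long-run delta, the analysis is outside the gate, and 20 is a reasonable reading of the text. On its own, the unstated number is only a missing detail.

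None of this gives a reason to stay at 20 when a larger number is so cheap.

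**Conclusion.** The concern holds and is minor. M = 20 leaves Monte Carlo noise with an SD of 0.04-0.15 on the z scale in the test that opens the sequence, and nothing in the plan measures or limits it. It matters only for results near 0.05. At the planned effect it would put the reported and long-run answers on opposite sides of 0.05 in about 0.4-1.4% of trials for 3.2 mg and 1.0-3.9% for 2.4 mg. With 500 imputations both fall roughly five-fold. Confidence in the size is medium, because the dropout range is assumed and the effect comes from the earlier AUC model.

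**What to change.** - In Addendum 2, Change 6, replace 20 with a larger pre-specified number, for example 500, keeping the seed order. Noise falls as 1/sqrt(M): 100 cuts it by 1 - sqrt(20/100) = 55%, and 500 by 1 - sqrt(20/500) = 80%.
- Use the same number for the per-protocol repeat of this analysis.
- State that number beside seed 456 for the tipping-point analysis.
- Report sqrt(B/M) beside the pooled estimate and p-value. Standard pooling already produces B.

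The cost is a short further SAP revision and computing time: 500/20 = 25 times as many model fits on about 600 subjects by 7 days. Estimand, model and alpha do not change. The change must be made before unblinding, since raising M after seeing a borderline p would look like choosing the result.
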